- Duration of remission (DoR) is defined as the time from the date of first documented CR or CRi to the date of death or relapse. For subjects who remain alive and have not relapsed following remission, DoR will be censored on the date of last relapse-related assessment prior to the initiation of alternative anti-cancer therapy.
- The primary ECG endpoint is Δ QTcF, the change from baseline in QTcF, the QT interval normalized using Fridericia's heart rate correction. Other endpoints include QTcF, QT, QRS, PR, HR (heart rate), and QTcB as well as Δ QT, Δ QRS, Δ PR, Δ HR (heart rate), Δ QTcB, the associated changes from baseline. (Note: QTcB is the QT interval normalized using Bazett's hear rate correction.)
- Overall survival (OS) will also be summarized. OS is defined as the time between the first date of treatment and the date of death due to any cause. A subject who has not died will be censored at the last known alive date.

Analyses:

Safety Analysis:

All recorded AEs will be listed and tabulated by system organ class, preferred term and treatment. Vital signs, clinical laboratory test results and any significant physical examination findings will be listed and summarized by treatment. ECG readings will be evaluated by the Investigator and abnormalities, if present, will be listed. To assess the effects of ulocuplumab on heart rate, PR, QRS, QT, QTcF, and Δ QTcF intervals, the frequency distribution for maximum QTcF, PR, QRS and the maximum Δ QTcF will be tabulated. For QTcF a linear regression of Δ QTcF on drug concentration will be estimated. Summary statistics will be tabulated for all ECG parameters and changes from baseline. The plots of mean and mean changes from baseline versus time or ulocuplumab concentration may be provided. A two-sided 90% confidence interval will be constructed for the population mean of Δ QTcF at each time point.

PK Analysis:

Summary statistics will be tabulated for the PK parameters and RO by treatment and study day. Geometric means and coefficients of variation will be presented for C_{max}, AUC and CL. Medians, minimum, and maximum will be presented for T_{max}. Means and standard deviations will be provided for the remaining PK parameters. Individual as well as mean concentration-time plots will be depicted.

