3.4.2 Prohibited and/or Restricted Treatments

Prohibited and/or restricted medications taken prior to ulocuplumab administration in the study are described below. Medications taken within 4 weeks prior to ulocuplumab administration must be recorded on the CRF. Any concomitant medications (prescription, over-the-counter or herbal) administered during the study must be recorded on the CRF.

The following therapies are **prohibited** during the study:

- a) Concomitant use of other systemic anti-cancer therapy may not be used while the subject is participating in the study except the follow-up period. Radiation therapy for bone pain will be discussed with the BMS Medical Monitor. No new investigational therapies for any reason shall be initiated while the subject is participating in the study.
- b) Subjects taking oral or parenteral corticosteroids must be tapered off this medication prior to the first dose of ulocuplumab and must remain discontinued from all oral and parenteral corticosteroids while participating in the study except the follow-up period (unless used for treatment of infusion reactions, rash or antiemetic prophylaxis or subjects on low-dose corticosteroids [< 20 mg prednisone or equivalent] for chronic conditions. Investigators should discuss individual cases with the BMS Medical Monitor).
- c) Concomitant use of medications which may prolong QT intervals are prohibited during Cycle 1 and 2 in subjects participating the serial QTc assessment (Serial PK/ECG Subset). A list of prohibited drugs that prolong QTc will be provided in a separate study guidance document.

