3.5 Discontinuation of Subjects from Treatment

Subjects **MUST** discontinue investigational product (and non-investigational product at the discretion of the investigator) for any of the following reasons:

- Subject's request to stop study treatment
- Any clinical adverse event (AE), laboratory abnormality or intercurrent illness which, in the opinion of the investigator, indicates that continued participation in the study is not in the best interest of the subject
- Termination of the study by Bristol-Myers Squibb (BMS)
- Loss of ability to freely provide consent through imprisonment or involuntarily incarceration for treatment of either a psychiatric or physical (eg, infectious disease) illness
- Withdrawal of informed consent (subject's decision to withdraw for any reason)
- Pregnancy
- Inability to comply with protocol
- Discretion of the investigator
- Disease progression
- New extramedullary disease
- Elective stem cell transplant (SCT)
- Subject is lost to follow up
- Death
- DLT
- AEs which require discontinuation according to [Section 4.6.1](#)
- Need for any treatment not allowed by the protocol.

In the case of pregnancy, the investigator must immediately notify Sponsor or designee of this event. In most cases, the study drug will be permanently discontinued in an appropriate manner. Please contact the Sponsor or designee within 24 hours of awareness of pregnancy. If the investigator determines a possible favorable benefit/risk ratio that warrants continuation of study drug, a discussion between the investigator and the Sponsor or designee must occur.

All subjects who discontinue study drug should comply with protocol specified follow-up procedures as outlined in [Section 5](#). The only exception to this requirement is when a subject withdraws consent for all study procedures including post-treatment study follow-up or loses the ability to consent freely (ie, is imprisoned or involuntarily incarcerated for the treatment of either a psychiatric or physical illness).

If study drug is discontinued prior to the subject's completion of the study, the reason for the discontinuation must be documented in the subject's medical records and entered on the appropriate case report form (CRF) page.

If a subject was withdrawn before completing the study, the reason for withdrawal must be entered on the appropriate CRF page.

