2.4 Blinding and Unblinding

The study is open-label.

Unblinded reports of interim data will be available to the DMC, without the use of fully- or partially-blinded treatment codes. Treatment codes will be provided by the BMS randomization coordinator to the reporting statistician after the database lock for the DMC analyses. Interim results for this exploratory study (for which there will be no inferential testing between treatment groups) will be available for review by a limited number of BMS personnel for planning purposes. Protocol Amendments

There are currently 7 amendments. The history of protocol amendments is summarized in the table below.

Table 2: Protocol Amendments

Amendment	Date	Main changes
1	24 Oct 2014	Clarifications in response to the PMDA review for Clinical Trial Notification
2	7 May 2015	Removal of restriction on AML (newly diagnosed, elderly); modification of prior therapy-related criteria and hepatitis B and C infection criteria
3	2 Nov 2016	Addition of randomized expansion cohort, with primary objective to assess preliminary efficacy; clarification of Phase 2 secondary objectives (safety and tolerability, overall remission [OR], CR/CRi, duration of remission [DoR], OS); added exploratory objectives (receptor occupancy [RO] and biomarkers)
4 (Brazil only)	19 Jan 2017	Clarification of post-study access to therapy in Brazil
5	10 Feb 2017	Addition of central laboratory cytogenetic testing; clarification of dosing and study assessment details
6	29 Mar 2017	Clarification of Phase 2 design (as exploratory, non-comparative; primary analysis to be conducted after all patients had opportunity for 6 months of follow-up; clarified that DoR will be censored on the date of last relapse-related assessment prior to the initiation of alternative anti-cancer therapy); increased local laboratory window allowances for hematology, chemistry and urinalysis to 72 hours; clarification of dose modifications and dose delays; clarification of study design; addition of whole exome sequencing to bone marrow and peripheral blood biomarker testing; added ECG, biomarker, cytogenetic and molecular analysis sections.
7	27 Jul 2017	Revision of exclusion criteria to specify allogeneic transplants in patients who received prior hematopoietic stem cell transplantation; clarification of hematology sampling schedule during cycles 1 and 2; revision of peripheral

		blood and serum/plasma collection criteria during end-of-study treatment and follow-up assessments.

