4.1 Efficacy Endpoints

4.1.1 Primary Endpoint

- Rate of complete remission (CR/CRi), prior to the initiation of any alternative therapy (including any subsequent ulocuplumab 800 mg for subjects in the LDAC alone arm). Response will be assessed by the investigator in accordance with the 2003 International Working Group (IWG) response criteria. The primary analysis will be conducted after all patients have had opportunity for 6 months of follow-up.

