4.1.2 Secondary Endpoints

- Rate of OR (= PR + CR + CRi)
- DoR: the time from the date of first documented CR/CRi to the date of death or relapse. For subjects who remain alive and have not relapsed following remission, DoR will be censored on the date of last relapse-related assessment prior to the initiation of alternative anti-cancer therapy.
- OS: the time between the first date of treatment and the date of death due to any cause. A subject who has not died will be censored at the last known alive date.

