7.5.2 Overall Survival

OS will be estimated using Kaplan Meier (KM) methodology. Median OS will be estimated, along with two-sided 95% CIs using the Brookmeyer and Crowley method, considering a log-log transformation.

- KM plot of OS

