7.5.3 Duration of Remission

For subjects who achieve CR or CRi, DoR will be estimated in the same way as OS.

- KM plot of DoR

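### Duration of remission is cut at alternative therapy only for remitters who stay alive and relapse-free, so as worded censoring depends on a later outcome (minor, cheap to correct)

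*SAP*

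**What the plan says.** SAP 4.1.2 measures DoR from the first documented CR or CRi to relapse or death. It does not limit events to those before other therapy. The one censoring sentence begins "For subjects who remain alive and have not relapsed following remission, DoR will be censored on the date of last relapse-related assessment" and dates that assessment before alternative anti-cancer therapy starts. Protocol 8.3.2 and the protocol synopsis carry the same rule: "DoR will be censored on the date of last relapse-related assessment prior to the initiation of alternative anti-cancer therapy", again only for subjects who are alive without relapse.

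The analysis sections add no censoring rule. SAP 7.5.3 states: "For subjects who achieve CR or CRi, DoR will be estimated in the same way as OS". For OS, SAP 7.5.2 states: "OS will be estimated using Kaplan Meier (KM) methodology". Protocol 8.4.2 likewise gives only Kaplan-Meier. Neither document says what happens to a remitter who starts other therapy and then relapses or dies.

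Two places hint at what was meant. SAP Table 2, on Amendment 6, reports the change without the alive-and-relapse-free condition: "clarified that DoR will be censored on the date of last relapse-related assessment prior to the initiation of alternative anti-cancer therapy". The primary endpoint in SAP 4.1.1 stops at other therapy for every subject: "Rate of complete remission (CR/CRi), prior to the initiation of any alternative therapy". These are signs of intent. An amendment summary that differs from the operative text is not an error in itself.

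**The concern.** Take two remitters who both start other therapy at month 4. One dies at month 10 and, as worded, is an event at month 10. The other is alive at month 20 and is censored at or before month 4. Months 4 to 10 count for the first subject only because that subject died. Kaplan-Meier needs the decision to censor at a given time to rest on what is known by then. Here it rests on what happens afterwards.

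The sentence blends two rules, each of which applies alike to every remitter: stop everyone at other therapy, or follow everyone through it. As worded, the deaths of switchers stay in and the event-free time of surviving switchers drops out. A programmer who follows the sentence literally and one who follows the apparent intent would build different DoR datasets. Protocol 3.6 calls OS and DoR key to the study, and SAP 3.2 sets the LDAC-alone results beside historical controls. Both uses need a clear rule.

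**Working it through.** **1. Planning figure and number of remitters.** The only planning figure is the exact 95% CI with 40 subjects per arm (SAP 5); none is given for DoR. Clopper-Pearson gives 0.433-0.751 for 24/40 and 0.293-0.615 for 18/40, which matches the plan's 0.43-0.75 and 0.29-0.62. Remitters per arm are therefore 40 x 0.45 = 18 to 40 x 0.60 = 24.

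**2. Hand example (invented data).** There are ten remitters. Six never switch: they relapse at months 3, 5, 8 and 10, and two are censored at 12. Four switch at month 4: two die at months 7 and 9, and two are alive at 12. The last assessment before the switch is taken as month 4. Kaplan-Meier after month 10:

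- As written: 9/10 x 6/7 x 5/6 x 4/5 x 3/4 x 2/3 = 0.257
- All four censored at month 4: 9/10 x 4/5 x 3/4 x 2/3 = 0.36
- Everyone followed through: 9/10 x 8/9 x 7/8 x 6/7 x 5/6 x 4/5 = 0.40

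The wording gives the lowest value.

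**3. Large-sample size.** All inputs are assumptions, because the documents give no switching rate.

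- R, time to first relapse or death: exponential, median 8 or 12 months; 20% of first events are deaths.
- Survival after relapse: exponential, median 3, 6 or 9 months.
- A, time to other therapy: exponential, median 12, 24, 36 or 60 months.
- C, data cut: uniform from 3 to 21 months.
- As written: event at R if R <= min(A, C). If A comes first, event at death if death <= C, otherwise censored at A. After a switch only deaths are seen.
- Uniform rule: censored at A whenever A comes first.

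| Setting | Share switching | True median | As written | Uniform rule |
|---|---|---|---|---|
| Switching unrelated to risk | 8-31% | 8 | 7.73-7.97 | about 8.0 |
| Switching unrelated to risk | 9-35% | 12 | 10.65-11.81 | about 12.0 |
| Higher-risk switch sooner* | 7-27% | 9.6 | 9.4-9.8 | 9.8-10.9 |
| Higher-risk switch sooner* | 8-31% | 14.3 | 12.8-14.3 | 14.9-17.3 |

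*A shared gamma frailty (shape 2) multiplies both hazards.

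In the first two rows the shortfall is 8 - 7.97 = 0.03 to 8 - 7.73 = 0.27 months, and 12 - 11.81 = 0.19 to 12 - 10.65 = 1.35 months. Twelve-month DoR reads 31-35% against 35%, and 45-49% against 50%. With no switching the effect is zero.

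**4. One arm of 18 to 24 remitters, switching unrelated to risk.** On average 1.4-8.4 switch first and 0.3-2.0 of these become late death events. The two rules differ by at least one month, or only one reaches a median, in 7-29% of simulated arms (true 8) and 9-36% (true 12). Sampling error is larger: as written, the 5th to 95th percentile of the estimated median runs from about 4 to 16 months (true 8), and from 6 months to not reached (true 12).

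**The case against.** The best defence is that this is a gap in wording, not a chosen method. The sponsor probably means to stop everyone at other therapy, and conventions are left to the data presentation plan, which is not among the documents. That is fair as to intent. A reader might infer that the sponsor decided to count deaths after a switch; the documents do not show that. The endpoint is nevertheless defined in the SAP and protocol, and their text does not state the uniform rule.

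The trigger is also limited. Subjects must be ineligible for transplant at entry (protocol 3.3.1), so elective transplant, although listed in protocol 3.5, should be rare. Other anti-cancer therapy is restricted: "Concomitant use of other systemic anti-cancer therapy may not be used while the subject is participating in the study except the follow-up period". Ulocuplumab added to LDAC alone follows relapse or failure to reach CR/CRi (protocol 3.1), so it should seldom begin in remission. The case remains possible, because subjects can stop without relapse on request, for an adverse event or at the investigator's discretion, and may then receive other therapy in follow-up.

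Two objections to the remedy stand. If higher-risk remitters switch sooner, the current wording lies closer to the true median than the uniform rule does, because two errors offset. That is no reason to keep an outcome-dependent rule, but the downside must be stated. Further, no marrow assessment is scheduled after the 30-day visit (protocol Table 5.1-3), so a non-switcher who dies later is an event while a survivor is censored earlier. Suppose nobody switches and assessments end one month after treatment stops. Either rule then gives 7.8-8.0 for a true 8 and 10.9-11.8 for a true 12. The correction leaves this separate asymmetry in place.

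**Conclusion.** The point holds on the text: in all three places the cut at other therapy is conditional on staying alive and relapse-free, so censoring depends on a later outcome. It is minor. DoR is secondary and descriptive, with no test between arms, and the design limits switching in remission.

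Under the assumed 8-35% switching unrelated to risk, the median reads low by about 0.03-0.3 months (true 8) or 0.2-1.4 months (true 12), well inside sampling error. A reader might infer that DoR will be materially understated. The documents do not support that: they give no switching rate, and if higher-risk remitters switch sooner the direction is not fixed.

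**What to change.** In SAP 4.1.2, protocol 8.3.2 and the synopsis, state one rule for every remitter:

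> A subject who starts alternative anti-cancer therapy before relapse or death is censored at the last relapse-related assessment before that start, regardless of later events; other subjects alive without relapse are censored at their last relapse-related assessment.

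This overstates DoR if higher-risk remitters switch sooner. So add one sensitivity analysis to SAP 7.5.3 that counts relapse or death regardless of other therapy, with event-free subjects who started other therapy censored at the last known alive date. Censoring them before the therapy would bring the present wording back.

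Do not call this analysis an upper bound. It tends to read high, because relapse after a switch is dated late (8.2-9.8 for a true 8 and 12.4-15.4 for a true 12, switching unrelated to risk). But it need not exceed the primary estimate: with higher-risk remitters switching sooner, a true median of 14.3 and a post-relapse median of 3 months, it reached 16.3 against 17.3 under the uniform rule at the highest switching rate. State also that deaths after relapse assessments have stopped remain a separate source of bias.

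The cost is one sentence in three places and one added analysis. No new data are needed: subsequent therapy is asked about every 3 months (protocol Table 5.1-3) and summarized (SAP 7.5.4), and the last known alive date already serves OS.

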8.2 Populations for Analyses

The following populations will be defined for each cohort.

- *All Enrolled Subjects*: All subjects who signed an informed consent form. Subject disposition will be tabulated using this dataset.
- *All Randomized Subjects* (Expansion Cohort only): All subjects who signed an informed consent form and were randomized to either ulocuplumab 800 mg or 1000 mg in combination with LDAC or to LDAC alone. This dataset will be used for baseline and efficacy analyses.
- *All Treated Subjects*: All subjects who received at least one dose of study medication (ulocuplumab in the combination arm and LDAC in the LDAC only arm). This dataset will be used for safety analyses (as well as some efficacy analyses).
- *PK Subjects*: All treated subjects who received at least one dose of ulocuplumab and have evaluable PK data.
- *Immunogenicity Subjects*: All subjects treated with ulocuplumab who have baseline and at least one post baseline immunogenicity assessment.

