- Duration of remission (DoR) is defined as the time from the date of first documented CR or CRi to the date of death or relapse. For subjects who remain alive and have not relapsed following remission, DoR will be censored on the date of last relapse-related assessment prior to the initiation of alternative anti-cancer therapy.
- The primary ECG endpoint is Δ QTcF, the change from baseline in QTcF, the QT interval normalized using Fridericia's heart rate correction. Other endpoints include QTcF, QT, QRS, PR, HR (heart rate), and QTcB as well as Δ QT, Δ QRS, Δ PR, Δ HR (heart rate), Δ QTcB, the associated changes from baseline. (Note: QTcB is the QT interval normalized using Bazett's heart rate correction.) The schedule for ECGs is given in [Table 5.5.1-1](#) (PK, RO, ADA, and ECG Sampling).
- Overall survival (OS) will also be summarized. OS is defined as the time between the first date of treatment and the date of death due to any cause. A subject who has not died will be censored at the last known alive date.

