6.2 Treatment Regimens

Unless otherwise specified, analyses will be performed by Phase 2 treatment arm:

- 1) ulocuplumab 800 mg in combination with LDAC 20 mg BID;
- 2) ulocuplumab 1000 mg in combination with LDAC 20 mg BID;
- 3) LDAC 20 mg BID alone.

Demographic and baseline characteristics, as well as (Phase 2) efficacy, will be summarized (in all randomized subjects) by treatment arm as randomized (per IWRS). Safety and exposure will be summarized (in all treated subjects) by treatment arm as treated. (In general, 'as treated' will be the same as 'as randomized'. However, if a subject received an incorrect drug for the entire period of treatment, the subject will be summarized according to the incorrect drug that the subject actually received.)

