6.3 Populations for Analyses

The following populations will be defined:

- *All Enrolled Subjects*: All subjects who signed an informed consent form and were registered into the IWRS. Subject disposition will be tabulated using this dataset.
- *All Randomized Subjects* (expansion cohort only): All subjects who signed an informed consent form and were randomized to either ulocuplumab 800 mg or 1000 mg in combination with LDAC or to LDAC alone. Demographic and baseline characteristics, as well as Phase 2 efficacy, will be summarized in all randomized subjects.
- *Response-evaluable subjects* (around 60 subjects at time of Interim Meeting #1): All randomized subjects who have opportunity to complete at least 2 cycles of treatment and

follow-up during the expansion phase. This will be the basis of some Phase 2 efficacy analyses in DMC Interim #2.

- *All Treated Subjects*: All subjects who received at least one dose of any study medication (ulocuplumab in the combination arm and LDAC in the LDAC only arm). Safety and exposure (as well as Phase 1 efficacy), will be summarized in all treated subjects.
- *PK Subjects*: All treated subjects who received at least one dose of ulocuplumab and have evaluable PK data.
- *Immunogenicity Subjects*: All subjects treated with ulocuplumab who have baseline and at least one post-baseline immunogenicity assessment.

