7.3 Study Population

7.3.1 Subject Disposition

The following will be provided:

- Pre-randomized subject status summary (with number of subjects enrolled, randomized, not randomized - with reason)
- Pre-treated subject status listing (with randomization date, treated, reason not treated)
- End of treatment period subject status summary (numbers continuing/not continuing in treatment period - with reason, continuing/not continuing in study - with reason)
 - For LDAC-alone subjects who enter a period of ulocuplumab treatment, the status of this added treatment will similarly be summarized:
 - ◆ End of added ulocuplumab period subject status summary
- End of treatment period subject status listing (continuing in treatment period, reason not continuing, continuing in study)
- End of follow-up subject status summary (numbers continuing/not continuing to be followed - with reason)
- End of follow-up subject status listing (continuing to be followed, not continuing - with reason)

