7.5 Efficacy

7.5.1 Complete Remission Rate and Other Response Endpoints

The rate of subjects with complete remission (CR/CRi) will be summarized by a binomial response rate, and corresponding two-sided 95% exact CI using the Clopper and Pearson method. This will be based on best overall response prior to the initiation of any alternative therapy (including any subsequent ulocuplumab 800 mg for subjects in the LDAC alone arm). The rate will be based on all randomized subjects, except at DMC Interim #2, when the calculation will be based on response-evaluable subjects. The rate of OR (= CR/CRi/PR) will similarly be summarized.

- Best response and remission rates summary (best response categorization [CR, CRi, PR, TF]; rates of complete and overall remission)
- Best response listing (with overall response by visit, best response)
- Bone marrow blast assessments plot (% change from baseline)
- Bone marrow blast assessments listing (with bone marrow blast [%], % change from baseline, best reduction, presentation of Auer rods by visit)
- Extramedullary disease listing (disease presence and disease site)
- RBC transfusion listing (type of transfusion)

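### Expansion-cohort OS is timed from first dose but reported in all randomized subjects, so a randomized subject who is never dosed has no OS time

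*SAP*

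**What the plan says.** **Time origin.** SAP 4.1.2 gives "OS: the time between the first date of treatment and the date of death due to any cause". Protocol 8.3.2, repeated in the synopsis, gives "OS is defined as the time between the first date of treatment and the date of death due to any cause". Subjects not known to have died are censored when last known alive.

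**Population.** SAP 4.1.2 lists OS among the Phase 2 efficacy endpoints. SAP 6.3 states: "Demographic and baseline characteristics, as well as Phase 2 efficacy, will be summarized in all randomized subjects". SAP 6.2 adds that the grouping is as randomized. Protocol 8.2 says of the All Randomized set: "This dataset will be used for baseline and efficacy analyses". For the treated set, SAP 6.3 says: "Safety and exposure (as well as Phase 1 efficacy), will be summarized in all treated subjects". SAP 7.5.2, the OS analysis section, names no population, no other start date and no rule for untreated subjects.

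**Never-dosed subjects.** Assignment through IWRS is a separate step after screening (Protocol 4.5). SAP 7.3.1 plans a listing that allows for randomized subjects who do not start treatment: "Pre-treated subject status listing (with randomization date, treated, reason not treated".

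**Survival follow-up.** Protocol 5.4.2 asks sites to make every effort to obtain survival data on all randomized subjects. The contacts themselves are every 3 months after visit X01 (Table 5.1-3), and X01 is timed from the last dose (Protocol 3.1, Follow-up).

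**The concern.** The definition and the population cannot both be applied. A subject without a first dose has an end date (death, or last known alive) but no start date. The natural outcome in programming is a missing OS time and removal from the Kaplan-Meier estimate. A death between randomization and first dose would then appear in the death listing (SAP 7.6.1) but not as an OS event.

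Two things are at stake. First, an estimate described as covering all randomized subjects would in effect cover only treated ones. The trial is open-label, so whether a subject starts treatment can depend on the arm assigned, and the exclusions need not be alike across arms. Second, the contact schedule hangs on the last dose, so a never-dosed subject has no scheduled survival contact. Follow-up that was not collected cannot be recovered at analysis.

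Protocol 3.6 calls OS and duration of remission key, and SAP 2.1 plans a separate study-completion analysis to look at mature OS.

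**Working it through.** **1. The plan's own figure.** The only design figure is the exact 95% interval for CR/CRi with 40 per arm. Clopper-Pearson gives 0.4333 to 0.7514 for 24/40 and 0.2926 to 0.6151 for 18/40. These round to the stated 0.43-0.75 and 0.29-0.62. The figures are right, and the OS point does not depend on them. No OS figure is stated, so there is none to reproduce.

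**2. The rules applied to one subject.** Consider a subject randomized, never dosed, who dies.

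| Rule | Source | Result |
|---|---|---|
| In the OS population? | SAP 6.2, 6.3; Protocol 8.2 | Yes |
| OS start date | SAP 4.1.2; Protocol 8.3.2 | None exists |
| OS end date | Same | Date of death |
| OS time | End minus start | Not computable |
| In the death listing? | SAP 7.6.1 (all enrolled subjects) | Yes |
| Scheduled survival contact | Protocol 3.1; Table 5.1-3 | None, because there is no last dose |

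**3. Size, one-month mortality.** From the documents: n = 40 per arm. Assumed: 4 deaths in the first month among dosed subjects, and k never dosed, with k from 1 to 4. Time from randomization to first dose is ignored for dosed subjects, which isolates the effect of exclusion.

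- As written: 4/(40 − k)
- From randomization, all k alive at one month: 4/40
- From randomization, all k dead by one month: (4 + k)/40

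| k | As written | All k alive | All k dead |
|---|---|---|---|
| 1 | 4/39 = 10.3% | 10.0% | 5/40 = 12.5% |
| 2 | 4/38 = 10.5% | 10.0% | 6/40 = 15.0% |
| 3 | 4/37 = 10.8% | 10.0% | 7/40 = 17.5% |
| 4 | 4/36 = 11.1% | 10.0% | 8/40 = 20.0% |

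**4. Direction.** Let m be mortality among the never dosed. The two figures agree when (4 + km)/40 = 4/(40 − k), which solves to m = 4/(40 − k), the dosed mortality itself (10.3% to 11.1%). Above that value the plan's rule flatters survival; below it, the rule understates survival. With k = 0 no subject is lost.

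**5. Size, six-month survival.** Assume 0.50 among dosed subjects. With 2 of 40 never dosed, the all-randomized value lies between (0.50 × 38)/40 = 0.475 and (0.50 × 38 + 2)/40 = 0.525. With 4 of 40 it lies between (0.50 × 36)/40 = 0.45 and (0.50 × 36 + 4)/40 = 0.55.

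**6. Would it arise?** If each of 120 subjects independently has chance q of never being dosed, the probability of at least one is 1 − (1 − q)^120. That is 0.70 at q = 1% (1.2 expected), 0.95 at 2.5% (3 expected) and 0.998 at 5% (6 expected). These rates are assumptions; the documents give none.

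**The case against.** The best counter-argument is that treated-only OS was meant. The OS objectives speak of subjects treated with each regimen, and Protocol 8.2 lets the treated set serve some efficacy analyses. A first-dose origin fits that reading. But the primary objective also speaks of treated subjects, and its endpoint is analysed otherwise (SAP 7.5.1): "The rate will be based on all randomized subjects, except at DMC Interim #2". Protocol 8.2 does not name OS, and SAP 6.3 confines treated-set efficacy to Phase 1. Treated-only OS would be coherent if declared, but it is not declared.

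On follow-up, Protocol 3.1 also says without condition that subjects are followed for survival for 2 years, and Protocol 5.4.2 covers all randomized subjects who are eligible and have not withdrawn consent for survival data. So collection is required in principle. What is missing is an anchor for the contacts.

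A handling rule could sit in the Data Presentation Plan, to which SAP 8 and 9 refer and which is not available here. That would not reconcile the endpoint definition with the population in the protocol and SAP.

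Three points stand:

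- The size is assumed throughout, and sampling error is large: the exact 95% interval for 4/38 is 2.9% to 24.8%, which contains every value in the one-month table.
- OS is secondary and descriptive in a non-comparative cohort with no between-arm testing.
- The disposition and death listings would let a careful reader find the excluded subjects.

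These limit the consequence; they do not make the rule workable.

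**Conclusion.** The concern holds. The OS definition cannot be applied to every member of the population assigned to it, and following the plan literally turns an all-randomized OS into a treated-only one without saying so. It should be fixed before the OS analysis.

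Neither the size nor the direction of any bias can be known from the documents. Both depend on how many randomized subjects are never dosed and how they fare relative to dosed subjects. Under the assumptions above, with 2 of 40 never dosed, one-month mortality moves from 10.5% to anywhere between 10.0% and 15.0%. The primary CR/CRi rate at the final analysis is untouched.

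**What to change.** For the expansion cohort:

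- In Protocol 8.3.2, its synopsis copy and SAP 4.1.2, define OS as running from the date of randomization to death from any cause. Count deaths of never-dosed subjects as events, and censor only subjects not known to have died, when last known alive.
- In SAP 7.5.2, name all randomized subjects, by assigned arm, as the OS population.
- In Protocol 3.1 and Table 5.1-3, state that the 3-monthly survival contacts also apply to randomized, never-dosed subjects, in line with Protocol 5.4.2.

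Keep first dose as time zero for the escalation cohort, which was not randomized.

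If the sponsor does intend treated-only OS, SAP 6.2, 6.3 and 7.5.2 must say so, and the number excluded must be reported by arm.

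The cost is low. The randomization date is already listed (SAP 7.2.1 and 7.3.1), and Table 5.1-3 allows contacts by phone. The text changes are a sentence or so in each place, though the protocol edits need ethics committee approval (Protocol 9.1.1).
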